8.2.10. Hepatitis C Testing and Monitoring

Initial testing for HCV infection includes testing for antibodies to HCV.

If	Then
anti-HCV is positive	HCV RNA testing is required.
HCV RNA test is negative	the participant is not excluded.
HCV RNA test is positive	the participant is excluded.

Participants who have had HCV infection and have been successfully treated must also have a negative HCV RNA test at screening to remain eligible for the study. Successful treatment is defined as a sustained virologic response of HCV RNA by PCR negative for at least 24 weeks following treatment completion.

If HCV RNA is detected during the study, the study intervention will be permanently discontinued (Section 7.1), and the participant should receive appropriate follow-up medical care.

8.3. Adverse Events, Serious Adverse Events, and Product Complaints

The definitions of the following events can be found in Section 10.3, Appendix 3:

- AEs
- SAEs, and
- PCs.

These events will be reported by the participant, or, when appropriate, by a caregiver, surrogate, or the participant's legally authorized representative.

The investigator and any qualified designees are responsible for detecting, documenting, and recording events that meet these definitions and remain responsible for following up events that are serious, considered related to the study intervention or study procedures, or that caused the participant to discontinue the study intervention or the study (see Section 7).

Care will be taken not to introduce bias when detecting events. Open-ended and non-leading verbal questioning of the participant is the preferred method to inquire about event occurrences.

After the initial report, the investigator is required to proactively follow each participant at subsequent visits or contacts. All SAEs and AEs of special interest will be followed until resolution, stabilization, the event is otherwise explained, or the participant is lost to follow-up (as defined in Section 7.3). For PCs, the investigator is responsible for ensuring that follow-up includes any supplemental investigations as indicated to elucidate the nature or causality. Further information on follow-up procedures is provided in Section 10.3.

8.3.1. Timing and Mechanism for Collecting Events

This table describes the timing, deadlines, and mechanism for collecting events.

Event	Collection Start	Collection Stop	Timing for Reporting to Sponsor or Designee	Mechanism for Reporting	Back-up Method of Reporting
Adverse Event					
AE	Signing of the ICF	Participation in study has ended	As soon as possible upon site awareness	AE CRF	N/A
Serious Adverse	Event				
SAE and SAE updates – prior to start of study intervention and deemed reasonably possibly related to study procedures	Signing of the ICF	Start of intervention	Within 24 hours of awareness	SAE CRF	SAE paper form

Event	Collection Start	Collection Stop	Timing for Reporting to Sponsor or Designee	Mechanism for Reporting	Back-up Method of Reporting
SAE and SAE updates – after start of study intervention	Start of intervention	Participation in study has ended	Within 24 hours of awareness	SAE CRF	SAE paper form
SAE ^a – after participant's study participation has ended and the investigator becomes aware	After participant's study participation has ended	N/A	Promptly	SAE paper form	N/A
Pregnancy					
Pregnancy in female participants and female partners of male participants	After the start of study intervention	at least 5 terminal half- lives after the last dose	Within 24 hours (see Section 8.3.2)	Pregnancy paper form	Pregnancy paper form
Product Complain	ints				•
PC associated with an SAE or might have led to an SAE	Start of study intervention	End of study intervention	Within 24 hours of awareness	PC form	N/A
PC not associated with an SAE	Start of study intervention	End of study intervention	Within 1 business day of awareness	PC form	N/A
Updated PC information		_	As soon as possible upon site awareness	Originally completed PC form with all changes signed and dated by the investigator	N/A
PC (if investigator becomes aware)	Participation in study has ended	N/A	Promptly	PC form	

Abbreviations: AE = adverse event; CRF = case report form; ICF = informed consent form; N/A = not applicable; PC = product complaint; SAE = serious adverse event

^a SAEs should not be reported unless the investigator deems them to be possibly related to study treatment or study participation.

8.3.2. Pregnancy

Collection of pregnancy information

Male participants with partners who become pregnant

The investigator will attempt to collect pregnancy information on any male participant's female partner who becomes pregnant while the male participant is in this study. This applies only to male participants who receive study intervention.

After learning of a pregnancy in the female partner of a study participant, the investigator will

- obtain a consent to release information from the pregnant female partner directly,
 and
- within 24 hours after obtaining this consent will record pregnancy information on the appropriate form and submit it to the sponsor.

The female partner will also be followed to determine the outcome of the pregnancy. Information on the status of the mother and child will be forwarded to the sponsor. Generally, the follow-up will be no longer than 12 weeks following the estimated delivery date. Any termination of the pregnancy will be reported regardless of gestational age, fetal status (presence or absence of anomalies) or indication for the procedure.

Female participants who become pregnant

The investigator will collect pregnancy information on any female participant who becomes pregnant while participating in this study. The initial information will be recorded on the appropriate form and submitted to the sponsor within 24 hours of learning of a participant's pregnancy.

[figure not shown]
The participant will be followed to determine the outcome of the pregnancy. The investigator will collect follow-up information on the participant and the neonate and the information will be forwarded to the sponsor. Generally, follow-up will not be required for longer than 12 weeks beyond the estimated delivery date. Any termination of pregnancy will be reported, regardless of gestational age, fetal status (presence or absence of anomalies) or indication for the procedure.

While pregnancy itself is not considered to be an AE or SAE, any pregnancy complication or elective termination of a pregnancy for medical reasons will be reported as an AE or SAE.

[figure not shown]
A spontaneous abortion (occurring at \leq 20 weeks gestational age) or still birth (occurring at \geq 20 weeks gestational age) is always considered to be an SAE and will be reported as such.

Any post-study pregnancy related SAE considered reasonably related to the study intervention by the investigator will be reported to the sponsor as described in Section 8.3.1. While the investigator is not obligated to actively seek this information in former study participants, they may learn of an SAE through spontaneous reporting.

Any female participant who becomes pregnant while participating in the study will discontinue study intervention. If the participant is discontinued from the study, follow the standard discontinuation process and continue directly to the follow-up phase. The follow-up on the pregnancy outcome should continue independent of intervention or study discontinuation.

8.4. Pharmacokinetics

8.5. Pharmacodynamics

Immunogenicity will be assessed by a validated assay designed to detect and characterize ADA in the presence of peresolimab at a laboratory approved by the sponsor.

Antidrug antibodies may be further characterized for their ability to neutralize the activity of peresolimab.

Instructions for the collection and handling of blood samples will be provided by the sponsor.

Treatment-emergent ADAs are defined in Section 9.3.7.

Sample retention is described in Section 10.1.12.

8.9. Health Economics

Health economics or medical resource utilization and health economics parameters are not evaluated in this study.

9. Statistical Considerations

The SAP will be finalized prior to unblinding, and it will include a more technical and detailed description of the statistical analyses described in this section. This section is a summary of the planned statistical analyses of the most important endpoints, including primary and key secondary endpoints.

9.1. Statistical Hypotheses

9.1.1. Multiplicity Adjustment

Adjustment for multiple comparisons will not be employed in the analysis for this study.

9.2. Analyses Sets

9.3. Statistical Analyses

9.3.1. General Considerations

Statistical analysis of this study will be the responsibility of sponsor or its designee. A detailed SAP describing the statistical methodologies will be developed by the sponsor or its designee.

Handling of missing, unused, and spurious data are addressed prospectively in the overall statistical methods described in the protocol and in the SAP, where appropriate. Adjustments to the planned analyses are described in the final CSR.

Efficacy analyses will be conducted on the mITT population, unless otherwise specified. Safety analyses will be conducted on the safety population. Placebo participants will be pooled for

This study includes

- Period I screening period
- Period II CC double-blind, placebo-controlled treatment period
- Period III CC double-blind treatment period, and
- Period IV post-treatment follow-up.

Efficacy and safety data will be analyzed and summarized by these treatment periods if appropriate

Period II - double-blind, placebo-controlled treatment period
 Period III - double-blind treatment period.
 CCI
 CCI
 CCI

Baseline for the Treatment Period is defined as the last non-missing assessment on or prior to the date of the CC of study treatment. Any assessment collected after the CC is defined as post-baseline for the Treatment Period. Change from baseline will be calculated as the visit value of interest minus the baseline value. If a baseline value or the value at the visit is missing for a particular variable, then the change from baseline is defined as missing.

Summary statistics for continuous variables may include mean, standard deviation, median, and minimum and maximum values.

Categorical variables will be presented as counts and percentages. Variables will be analyzed in the original scale on which they are measured, unless otherwise specified.

The parametric approach will be employed by default for statistical analysis except when nonparametric analysis, such as by a rank-based method, is more fitting.

Additional exploratory analyses of the data will be conducted as deemed appropriate.

Dichotomous responder endpoints including the primary endpoint will be analyzed using a **CC**

The odd ratio and p-value based on odd ratio will be reported. CCI of mean difference will also be reported without being adjusted by covariates. Missing data will be imputed using the nonresponder imputation method.

Treatment comparisons of continuous efficacy endpoints with multiple postbaseline timepoints will be analyzed using CCI will include

- treatment
- stratification factors
- baseline value
- visit, and treatment-by-visit interaction in the model as fixed factors, and
- participant as a random factor.

The covariance structure to model the within-participant errors will be unstructured. If the unstructured covariance matrix results in a lack of convergence, the heterogeneous Toeplitz covariance structure, followed by the CCI will be used.

The CC will be used to estimate the denominator degrees of freedom. Type III sums of squares for the LS means will be used for the statistical comparison. The 95% CI will also be reported. Missing data will be handled with the missing at random assumption. No additional imputation methods will be applied to the CC

Where appropriate, treatment comparisons of continuous efficacy endpoints will be analyzed using CCI modeled with treatment group, stratification factors, and baseline value as covariates. Type III sums of squares for the LS means will be used for statistical comparison between treatment groups. The LS mean difference, standard error, p-value, and otherwise specified, will also be reported. Missing data imputation method for the CCI model will the last observation carried forward.

Dose response modeling will be performed on the primary objective to assist in dose selection decisions. More details will be provided in the SAP.

Any change to the data analysis methods or imputation methods described in the protocol will require an amendment only if it changes a principal feature of the protocol. Any other change to the data analysis methods described in the protocol, and the justification for making the change, will be described in the SAP and the clinical study report. Additional exploratory analyses of the data may be conducted as deemed appropriate.

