- Endpoint: American College of Rheumatology (ACR) 20 at Week 12
- How to account for intercurrent events (ICEs): ICEs related to study intervention include the use of rescue or prohibited medication and early discontinuation (ED) from the study or study intervention. A composite strategy will be used for these types of ICEs. Specifically, participants with ICEs related to study intervention will be considered as treatment failure (having no change from baseline), that is, a nonresponder, after the first occurrence of these ICEs.
- Population-level summary: Difference in proportion of participants achieving response at Week 12 between each dosing regimen of peresolimab and placebo
- Rationale for estimand: The primary estimand strategy assumes that:

- o If a participant used any rescue or prohibited medication, the participant was not receiving sufficient benefits from study intervention.
- o If a participant early discontinued the study or study intervention, the participant experienced a burden of study intervention that outweighed its benefits.

Secondary estimand for categorical endpoints at Week 12

For secondary objectives that have categorical endpoints analyzed at Week 12, the clinical question of interest is:

What is the difference between peresolimab and placebo in the target patient population, in achieving a successful response at Week 12 without use of rescue or prohibited medications or discontinuing the study intervention?

The estimand is described by the following attributes:

- Population: Participants with moderately-to-severely active RA
- Endpoint(s): ACR50, ACR70, Disease Activity Score high-sensitivity C-reactive protein (DAS28-hsCRP) low disease activity (LDA), Disease Activity Score erythrocyte sedimentation rate (DAS28-ESR) LDA, Simplified Disease Activity Index (SDAI) LDA, Clinical Disease Activity Index (CDAI) LDA, DAS28-hsCRP remission, DAS28-ESR remission, SDAI remission, and CDAI remission at Week 12
- How to account for ICEs: ICEs will be accounted using the same estimand strategy as for the primary estimand.
- Population-level summary: Difference in proportion of participants achieving response at Week 12 between each dosing regimen of peresolimab and placebo
- Rationale for estimand: Refer to the rationale for the primary estimand.

Secondary estimand for continuous endpoints at Week 12

For secondary objectives that have continuous endpoints analyzed at Week 12, the clinical question of interest is:

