For analyses in Period 2, participants randomized to either Placebo subcutaneous (SC) Q4W to Peresolimab 400 mg SC Q4W or Placebo SC Q4W to Peresolimab 1000 mg SC Q4W will be combined as Placebo SC Q4W.

Dichotomous efficacy endpoints including the primary endpoint during Period 2 will be analyzed using a CCI

Period 2, an estimate of the treatment difference with corresponding Wald 95% confidence interval (CI), the odds ratio with corresponding Wald 95% CI and p-value will be presented. Each treatment group will be compared to Placebo SC Q4W.

Continuous efficacy endpoints, which are planned to be collected at >1 postbaseline timepoints during Period 2 according to the SoA, will be analyzed using mixed-effect model for repeated measures (MMRM) analysis. The MMRM model will include:

- treatment, stratification factors, baseline value, visit and treatment-by-visit interaction in the model as fixed factors, and
- participant as a random factor.

The least squares (LS) mean for each treatment group along with the estimate of the difference between each treatment group with Placebo SC Q4W, standard error (SE), p-value, and the 95% CIs will be reported at each visit along with p-values.

The covariance structure to model the within-participant errors will be unstructured. If the unstructured covariance matrix results in a lack of convergence, the heterogeneous Toeplitz covariance structure, followed by the CCI, will be used.

The CCI will be used to estimate the denominator degrees of freedom.

Type III sums of squares for the LS means will be used for the statistical comparison. The 95% CI will also be reported.

When continuous efficacy endpoints are analyzed using CCI , the model will include treatment group, stratification factors, and baseline value as covariates. Type III sums of squares for the LS means will be used for statistical comparison between each treatment group and Placebo SC Q4W. The LS mean difference, SE, p-value, and 95% CI, unless otherwise specified, will also be reported.

Dose response modeling will be performed on the primary, and other core efficacy endpoints, if deemed necessary, to assist in dose selection decisions. More details will be provided in Section 4.2.

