Short Form-36 version 2 health survey acute form (SF-36v2)	The SF-36v2 Acute measure is a subjective, generic, health-related quality of life instrument that is patient-reported and consists of 36 questions covering 8 health domains: physical functioning, bodily pain, role limitations due to physical problems, role limitations due to emotional problems, general health perceptions, mental health, social function, and vitality. Each domain is scored by summing the individual items and transforming the scores into a 0 to 100 scale with higher scores indicating better health status or functioning. In addition, 2 summary scores, the physical component	 Physical Functioning Role Physical Bodily Pain General Health Vitality Social Functioning Role Emotional Mental Health 2 component Scores: MCS Score PCS Score 		
	score (PCS) and the mental component score (MCS), will be evaluated based on the 8 SF-36v2 Acute domains (McHorney et al. 1993; Ware et al. 2007; Ware and Sherbourne 1992; Maruish 2011).	Change from baseline in 8 associated domain scores and 2 component scores	Calculated as: Observed value – baseline value	Missing if baseline or observed value are missing.

Abbreviations: PGA = physician's global assessment; PatGA = patient's global assessment; RA = rheumatoid arthritis; SF-36 = Short Form-36 health survey acute form; SJC = swollen joint count; TJC = tender joint count.

Table KDAF.4.2. Description of Efficacy and Patient Reported Outcome Analyses

Measure	Variable	Estimand	Analysis Method	Population	Comparison and Timepoint	Analysis Type
American College of Rheumatology (ACR)	ACR20	Composite	Logistic with NRI	mITT	PER100Q4W vs. PBO; PER400Q4W vs. PBO; PER1000Q4W vs. PBO; At Week 12 and all other scheduled visits in Period 2	Primary analysis is at Week 12.
		Composite	Descriptive statistics with NRI	Maintenance	No between-treatment comparison; At Week 24 and all other scheduled visits in Period 3A	Secondary analysis is at Week 24.
		Composite	Descriptive statistics with NRI	Maintenance Primary; Maintenance Secondary; Maintenance Tertiary	No between-treatment comparison; At Week 60 and all other scheduled visits in Period 3B	Secondary analysis is at Week 60.
	ACR50/70	Composite	Logistic with NRI	mITT	PER100Q4W vs. PBO; PER400Q4W vs. PBO; PER1000Q4W vs. PBO; At Week 12 and all other scheduled visits in Period 2	Secondary analysis is at Week 12.

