6.8. Appendix 8: List of Geographic Region

Geographic region will be used as one of stratification factors for randomization at Week 0. Patients will be classified as one of the following geographic regions based on the sites where patients are enrolled: Europe, North America, and Other.

The list of countries in each geographic region are:

• Europe: Greece, Hungary, Poland, Spain

- North America: United States, Canada, and
- Other: Argentina, China, Japan, Mexico.

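### The primary estimand's risk difference is to be reported without adjustment for the randomisation strata, beside a p-value from the odds ratio: valid, but slightly less precise than it could be and not matched to the test

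*Protocol*

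**What the plan says.** - **Estimand.** SAP 1.1 gives the primary summary measure as "Difference in proportion of participants achieving response at Week 12 between each dosing regimen of peresolimab and placebo". Protocol section 3 also uses a difference in proportions.
- **Test.** Protocol 9.3.1, on dichotomous endpoints: "The odd ratio and p-value based on odd ratio will be reported". Table KDAF.4.2 of the SAP lists the primary method as "Logistic with NRI".
- **Difference.** Protocol 9.3.1 continues, after a redaction, "of mean difference will also be reported without being adjusted by covariates". SAP 4.1 lists "an estimate of the treatment difference with corresponding Wald 95% confidence interval (CI), the odds ratio with corresponding Wald 95% CI and p-value" and does not mention adjustment of the difference. The SAP introduction and SAP 4.9 both declare no change from the protocol's analyses.
- **Strata.** SAP Appendix 8: "Geographic region will be used as one of stratification factors for randomization at Week 0". The other factors are not visible. For continuous endpoints, Protocol 9.3.1 and SAP 4.1 put the stratification factors in the models.

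The covariates of the logistic model are redacted in both documents.

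**The concern.** Three things that should line up do not. The estimand is a risk difference. The p-value belongs to an odds ratio. The reported difference leaves out the factors on which randomisation was stratified.

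When strata predict response, stratified randomisation removes part of the chance variation between arms. The simple two-sample standard error does not credit that removal, so the interval for the estimand is a little wider than the design warrants. If the logistic model is adjusted, its odds ratio is also conditional on the strata while the difference is marginal, so the p-value and the interval describe different contrasts. In a dose-finding trial the size and precision of the effect by arm matter, so the estimate attached to the estimand should use what the design provides.

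**Working it through.** **Inputs from the documents.** SAP section 5 gives Week 12 group sizes of 60 (100 mg), 120 (400 mg), 120 (1000 mg) and 120 (pooled placebo). Their sum, 60 + 120 + 120 + 120 = 420, reproduces the stated total. No response rate, alpha or power is visible, so power cannot be reproduced.

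**Assumptions.** Placebo ACR20 of 25, 35 or 45%. Within-stratum odds ratio 2.25. Strata either three equal regions or a 70/30 split. The 70/30 split borrows the prior-therapy enrolment mix in the protocol synopsis; that it is a stratum is itself assumed. The placebo gap between highest and lowest stratum runs from 0 to 30 points.

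**Formulas.** Unadjusted variance = Pc(1−Pc)/nc + Pt(1−Pt)/nt, using overall rates. Stratified variance = the same expression with each P(1−P) replaced by its average within strata (balanced strata).

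**Worked case: three regions, placebo 25/35/45%, 120 v 120.**
- Odds ratio 2.25 gives treated rates of 42.9, 54.8 and 64.8%. Overall rates are 35.0 and 54.15%, a difference of 19.1 points.
- Unadjusted: (0.2275 + 0.2483)/120 = 0.003965; SE 0.0630; 95% half-width 12.3 points.
- Stratified: mean within-stratum terms are (0.1875 + 0.2275 + 0.2475)/3 = 0.2208 and (0.2449 + 0.2477 + 0.2281)/3 = 0.2402. (0.2208 + 0.2402)/120 = 0.003842; SE 0.0620; half-width 12.1 points.
- Excess variance: 0.4758/0.4610 − 1 = 3.2%.

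**Range over all assumed settings (both stratum layouts, 120 v 120 and 60 v 120).**

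| Placebo gap between strata | Excess variance of unadjusted difference |
|---|---|
| 0 points | 0% |
| 10 points | 0.6–1.3% |
| 20 points | 2.6–5.2% |
| 30 points | 6.2–12.1% |

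The top figure needs placebo at 25% and a 30-point gap. With placebo at 35%, the 30-point gap gives 7.6–8.6%.

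**Simulation (placebo 35%, 70/30 strata, 100,000 trials per scenario).** At a 20-point gap the true difference is 0.1903, and both estimators average 0.1904, so neither is biased. Coverage of the 95% interval at 120 v 120, odds ratio 2.25:

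| Gap | Unadjusted | Stratified |
|---|---|---|
| 0 | 95.1% | 94.9% |
| 20 points | 95.5% | 94.5% |
| 30 points | 96.0% | 94.6% |

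Under no effect at 120 v 120, the unadjusted difference rejects in 4.3–5.1% of trials and the stratified one in 5.2–5.5%. At 60 v 120 the figures are 4.3–5.5% and 5.6–5.7%.

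**Agreement of test and interval.** A within-stratum odds ratio of 2.25 corresponds to a marginal odds ratio of 2.06 to 2.25 over these settings, so an adjusted odds ratio and an unadjusted difference are not the same contrast. In 800 simulated trials per scenario (35% v 52%, 120 v 120, logistic model assumed to include the strata), the p-value and the unadjusted interval disagreed in 0.6–1.6% of trials, roughly 5 to 13 trials. In an extreme 60 v 120 case the figure reached 5%.

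**The case against.** **The unadjusted difference estimates the stated estimand directly.** This stands. It is unbiased, and coverage of 95.5–96.0% is not a defect. A reader might infer that the interval is invalid or the type I error inflated; the calculations show neither. An odds ratio of 1 and a difference of 0 coincide when there is no effect, so the odds-ratio test does address the null in SAP section 2.

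**The decisive text is partly redacted.** This stands in part. The start of the quoted sentence and the logistic model specification cannot be read, and the SAP does not itself call the difference unadjusted. That rests on the protocol sentence plus the SAP's statements of no change. A reader might infer that the strata are dropped from the hypothesis test and that power is lost. The documents do not support that: the logistic model may already contain the strata. In 4,000 simulated trials (35% v 52%, 120 v 120) with strongly predictive strata, rejection was 78.5% for the unadjusted difference, 80.5% stratified and 80.1% for an adjusted logistic test. With weak strata the figures were 78.1, 77.9 and 78.2%. Against an adjusted logistic test there is essentially nothing to gain in power.

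**The effect is small and depends on assumptions.** This stands. Region is the only visible factor, and if it barely predicts response the gain vanishes.

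**The dose decision leans on the Bayesian dose-response model, not on p = 0.05.** SAP 4.2 supports this, and no decision rule at that boundary is visible. It lowers the stakes of occasional disagreement. It does not remove the case for matching the primary estimand with its best available estimate.

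**Conclusion.** The point holds as a modest matter of efficiency and alignment, not as an error of validity. The plan defines the estimand as a risk difference, reports that difference unadjusted despite stratified randomisation, and takes the p-value from another measure. The continuous endpoints are treated differently, since their models carry the strata.

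The cost is about 0 to 10% excess variance (12% in the most extreme setting), or a few tenths of a percentage point on a half-width of about 12 points. With it come slight over-coverage and a small chance that interval and p-value disagree. These sizes rest on assumed response rates, odds ratio and stratum gaps. The disagreement figures also assume a stratum-adjusted logistic model. No gain in power over the planned test is claimed.

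**What to change.** Report the risk difference standardised over the randomisation strata as the estimate for the primary estimand, with its matching confidence interval. Either g-computation from the planned logistic model with a robust standard error, or Mantel-Haenszel weighting, would serve. Keep the odds ratio and the unadjusted difference as supportive. State in SAP 4.1 which covariates enter each quantity.

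Add a rule for pooling sparse strata. It is needed for the 60-participant 100 mg arm and for rarer endpoints such as ACR70 and remission, which fall under the same dichotomous-endpoint method.

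Timing matters. SAP version 2 was approved before the primary outcome lock, and version 3 is described only as preceding the final lock. If the primary data are already unblinded, the standardised difference should be added and labelled supplementary, not substituted for the planned result.

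The cost is SAP wording and a little programming, with no new data. The downside is small: the pooling rule itself, and coverage marginally below nominal (about 94–95%) where strata are small.
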